# APPENDIX 1 CLINICAL DIAGNOSTIC CRITERIA CLINICAL DIAGNOSTIC CRITERIA FOR PROS

D a graine de	Composited on Foulsy Childhood Ongot					
Required:	Congenital or Early Childhood Onset					
	Overgrowth Sporadic and Mosaic (Other terms: Patchy,					
	Irregular)					
	Presence of PIK3CA mutation in overgrowth lesion					
	Features described in either A or B					
A.	Overgrowth: Adipose, Muscle, Nerve, Skeletal					
Spectrum (2 or more)	Vascular Malformations: Capillary Venous, Arteriovenous					
	Malformation, Lymphatic					
	Epidermal Nevus					
В.	Large Isolated Lymphatic Malformation					
Isolated Features	Isolated Macrodactyly OR Overgrown Splayed Feet/Hands,					
	Overgrown Limbs					
	Truncal Adipose Overgrowth					
	Hemimegalencephaly					
	Epidermal Nevus					
	Seborrheic Keratoses					
	Benign Lichenoid Keratoses					

Keppler-Noreuil KM, et al. Am J Med Genet A. 2015 Feb;167A(2):287-95 [Keppler-Noreuil KM, Rios JJ, Parker VE, Semple RK, Lindhurst MJ 2015]

## **Clinical Diagnostic Criteria for Proteus Syndrome**

General Criteria	Specific Criteria			
All the following:	Either			
Mosaic distribution of lesions	Category A or,			
Sporadic occurrence	Two from category B or,			
Progressive course	Three from category C			
Specific criteria categories	Plus AKT1 mutation in overgrowth lesion			
Category A.	Category C			
Cerebriform connective tissue nevus	1. Dysregulated adipose tissue			
Category B.	Either one:			
1. Linear epidermal nevus	a) Lipomas			
2. Asymmetric, disproportionate overgrowth	b) Regional lipohypoplasia			
One or more:	2. Vascular malformations			
a) Limbs	One or more:			
b) Hyperostosis of the skull	a) Capillary malformation			
c) Hyperostosis of the external auditory canal	b) Venous malformation			
d) Megaspondylodysplasia	c) Lymphatic malformation			
e) Viscera:	3. Lung cysts			
f) Spleen/thymus	4. Facial phenotype (all of the following)			
3. Specific tumors before 2 nd decade	a) Dolichocephaly			
One of the following:	b) Long face			
a) Bilateral ovarian cystadenoma	c) Down slanting palpebral fissures and/or minor ptosis			
b) Parotid monomorphic adenoma	d) Low nasal bridge			
	e) Wide or anteverted nares			
	f) Open mouth at rest			

Biesecker L. Eur J Hum Genet. 2006 Nov;14(11):1151-7 [Biesecker, L. 2006].

## Definition of the Total Cerebriform Connective Tissue Nevus (CCTN) Lesional Area:

- The plantar surface of the foot is defined as CCTN, pre-CCTN and nonaffected area. The percentage of the affected area (total CCTN lesional area) is calculated based on the size of the sole, excluding toes
- Total lesional area is defined as the space encompassing CCTN and noncerebriform affected area
- The CCTN is defined as a nevus with at least 2 gyri and 3 sulci and should affect between 10% and 70% of the total surface area of the sole.

The pre-CCTN is defined as an area characterized by a confluent growth with visible papules and nodules but without typical nevus growths

## APPENDIX 2 DOSING NOMOGRAM

	15 mg/m² Dose Level									
BSA range (m  )	0.33-0.49	0.5- 0.82	0.83- 1.16	1.17- 1.49	1.50- 1.83	1.84- 2.16	2.17- 2.49	2.50- 2.83	≥2.84	
Target range (mg/day)	4.95-7.35	7.5- 12.3	12.45- 17.40	17.55- 22.35	22.50- 27.45	27.60- 32.40	32.55- 37.35	37.50- 42.45	≥42.60	
Actual Dose (mg qd)	5	10	15	20	25	30	35	40	45	
			25	mg/m  D	ose Leve	l				
BSA range (m  )	0.33-0.49	0.5	-0.69	0.70- 0.89	0.90- 1.09	1.1-1.29	1.30- 1.49	1.50- 1.69	≥1.70	
Target range (mg/day)	8.25- 12.25	12.5	-17.25	17.5- 22.25	22.5- 27.25	27.5- 32.25	32.5- 37.25	37.5- 42.25	≥42.5	
Actual Dose (mg qd)	10		15	20	25	30	35	40	45	

Target mg/day range = Desired dose level (eg,  $15 \text{ mg/m}^2 \text{ or } 25 \text{ mg/m}^2$ ) x BSA range (m^2)

Actual mg/m^2 dose range = Actual dose (mg) / BSA range(m^2)

Generally, a child of BSA  $0.5~m^2$  (the average BSA for a 2-year-old child) should receive 1/4 to 1/3 the dose in mg of that of an adult of BSA  $\sim 1.7~m^2$ . Hence, if the adult gets a 40-mg dose, the child should get a 10-mg dose.

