Miransertib will be supplied as 5 and 10-mg capsules, which should be taken either 1 hour before or 2 hours after a meal. Capsules should be swallowed whole. The preferred beverage for administration is water. However, in cases where there is a medical problem affecting the participant's ability to swallow (eg, the participant has an enlarged tongue), the capsules can be opened, and the powder contents sprinkled onto a small amount of sweetened semiliquid food (eg, apple sauce, chocolate syrup, or ice cream) and administered in its entirety to the participant. The same type of semiliquid food should be used, if possible, for the duration of the study. Refer to the Pharmacy Manual for specific instructions on opening the capsules. To maximize safety and avoid unnecessary exposure to the drug by caregivers, it is recommended that gloves and a facemask be worn by the caregiver when handling opened capsules and that the gloves and facemask are discarded along with the empty capsule shells after use. Pregnant women should not open the capsules.

Miransertib will be administered once daily. Dose will be calculated based on BSA, and actual dose level will be rounded to the nearest 5 mg using a dosing nomogram (Appendix 2). Miransertib will be capped at a BSA >1.77 m^2. During site visits, miransertib dosing will be adjusted for changes in BSA according to the dosing nomogram.

Participants and/or their guardians must use the diary card provided to keep a record of daily intake of each dose of miransertib and the method of administration (capsules swallowed whole or opened and swallowed with semiliquid).

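### The worked example in Appendix 2 (adult 40 mg, child of BSA 0.5 m² 10 mg) does not match the nomogram above it, which gives that child 15 mg at the 25 mg/m² level

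*Protocol*

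**What the plan says.** Protocol Appendix 2 has one table for the 15 mg/m² level and one for the 25 mg/m² level. Both rest on the rule "Target mg/day range = Desired dose level" multiplied by BSA. The dose rows read "Actual Dose (mg qd) 5 10 15 20 25 30 35 40 45" at 15 mg/m² and "Actual Dose (mg qd) 10 15 20 25 30 35 40 45" at 25 mg/m².

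The note below the tables says that a child of BSA 0.5 m², described as average for age two, "should receive 1/4 to 1/3 the dose in mg of that of an adult" of BSA about 1.7 m². It then gives one example: "Hence, if the adult gets a 40-mg dose, the child should get a 10-mg dose".

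Section 6.3 makes the nomogram the working tool: the "actual dose level will be rounded to the nearest 5 mg using a dosing nomogram (Appendix 2"), and at site visits "miransertib dosing will be adjusted for changes in BSA according to the dosing nomogram". For Part B Cohorts 1-3, Section 6.3 and Table 3 plan 15 mg/m² for three cycles and then, toxicity permitting, 25 mg/m² from Cycle 4 Day 1.

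**The concern.** The note and the tables share a page and give different mg doses for the same child. That child is eligible: Cohorts 1-3 admit participants from age 2 with BSA of at least 0.33 m². The example is worded as what the child should get, and Appendix 2 does not say whether the note or the table prevails.

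At stake is the dose of a very young participant at the planned 25 mg/m² step. The example's 10 mg is also the table's 15 mg/m² dose for this child, so the two sources can differ on whether the mg dose changes at Cycle 4. Safety and tolerability are the only remaining objective, and Protocol 9.1 and SAP 4.4 call for adverse events by dose within cohort. The mg dose behind each level should therefore be unambiguous.

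**Working it through.** **Inputs, all from Protocol Appendix 2**

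- Note: child BSA 0.5 m², adult BSA about 1.7 m², child/adult dose ratio 1/4 to 1/3, example 40 mg and 10 mg.
- 15 mg/m² table: BSA 0.5-0.82 gives 10 mg; 1.50-1.83 gives 25 mg; 2.50-2.83 gives 40 mg.
- 25 mg/m² table: BSA 0.33-0.49 gives 10 mg; 0.5-0.69 gives 15 mg; 1.50-1.69 gives 40 mg; 1.70 and above gives 45 mg.

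**Step 1: reproduce the tables.** Target = dose level × BSA. For example, 15 × 0.50 = 7.5 mg and 15 × 0.82 = 12.3 mg; 25 × 0.50 = 12.5 mg and 25 × 0.69 = 17.25 mg; 25 × 1.50 = 37.5 mg and 25 × 1.69 = 42.25 mg. Every printed target range is recovered from its BSA limits, so the tables are internally sound and a broken table extraction does not explain the mismatch.

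**Step 2: look up the note's child and adult.**

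| Level | Child 0.50 m² | Adult 1.69 m² | Adult 1.70 m² |
|---|---|---|---|
| 15 mg/m² | 7.5 → 10 mg | 25.35 → 25 mg | 25.5 → 25 mg |
| 25 mg/m² | 12.5 → 15 mg | 42.25 → 40 mg | 42.5 → 45 mg |

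No row contains 40 mg for the adult with 10 mg for the child. For an adult of about 1.7 m², 40 mg occurs only at the 25 mg/m² level. At 15 mg/m² it needs a BSA of 2.50-2.83 m².

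**Step 3: compare ratios with the note's 0.25 to 0.33.**

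- Note's example: 10/40 = 0.25.
- 25 mg/m² table, adult on 40 mg: 15/40 = 0.375, above 1/3. The note's range for a 40 mg adult is 40/4 = 10 mg to 40/3 = 13.3 mg, which does not reach 15 mg.
- 25 mg/m² table, adult of 1.70 m²: 15/45 = 0.333, at the upper limit and so consistent.
- 15 mg/m² table: 10/25 = 0.40, outside the range.
- Unrounded targets at either level: 0.5/1.7 = 0.294, inside the range.

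So the general ratio agrees with unrounded BSA scaling, and with the 25 mg/m² table at BSA 1.70. It fails against the rounded 15 mg/m² doses. At 25 mg/m² the firm conflict is with the 40/10 example.

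**Step 4: the band edge.** The child's 12.5 mg target is 2.5 mg from both 10 mg and 15 mg; the table assigns it to 15 mg. At BSA 0.49 m² the target is 12.25 mg and the table gives 10 mg.

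**Step 5: the consequence at BSA 0.5 m².**

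- Delivered dose: 10/0.5 = 20 mg/m² by the example, 15/0.5 = 30 mg/m² by the table.
- Table throughout: 10 mg in Cycles 1-3, then 15 mg, a step of +5 mg.
- Table in Cycles 1-3, then the example: 10 mg, then 10 mg, a step of 0 mg.
- Ratio rule from the start, with the table's 25 mg adult dose: 25/4 = 6.25 mg to 25/3 = 8.33 mg, rounding to 5 or 10 mg. A later 10 mg could then be an increase or no change.

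**The case against.** The strongest reply is that precedence is already settled. Section 6.3 tells sites to round and adjust with the nomogram, and Tables 3 and 4 require BSA and dose to be calculated at dispensing visits. The note opens with *Generally*, names no dose level and needs an adult comparator dose that a site treating a child would not have. This stands, and it limits the practical risk. It does not remove the conflict: Appendix 2, the page to which sites are sent, gives two mg figures for one child and no order of precedence.

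A second reply is that this is an edge effect, since moving each BSA down by 0.01 m² yields 40 mg and 10 mg within the 25 mg/m² table. The arithmetic is right, but the note specifies 0.5 m² and the table assigns 0.5 m² to 15 mg.

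Three stronger readings are tempting and are not supported:

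- A reader might infer that the example pairs a 25 mg/m² adult dose with a 15 mg/m² child dose. The edge calculation is an equally good explanation, and the documents do not show which applies.
- A reader might infer that any site using the note would make no increase at Cycle 4. That holds only if Cycles 1-3 were dosed from the table and the example was used afterwards.
- A reader might infer that such a child would be analysed at 25 mg/m² with the discrepancy hidden. SAP 4.4 does not say how dose is assigned in the adverse event summaries. SAP 4.12 computes the amount administered in mg from capsule counts, so an unchanged 10 mg dose would be visible in the exposure data.

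**Conclusion.** The inconsistency is real and exact at the stated BSA. The example gives 10 mg where the 25 mg/m² table gives 15 mg, a difference of one third of the table dose. The child/adult ratio also falls outside the note's range at the 15 mg/m² level (0.40), although only after rounding.

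The conclusion assumes that the example refers to the 25 mg/m² level, the only level at which an adult of about 1.7 m² receives 40 mg. The Cycle 4 consequence further assumes a change from table to example after Cycle 3. Nothing in the documents shows that a site has dosed from the note. The point should be corrected because it concerns the dose of an eligible young child in the operative dosing appendix, but its likely effect on the trial is small.

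**What to change.** The sponsor should reconcile the note with the nomogram: either remove the note and its example, or correct whichever of the two does not reflect the intended dosing. Appendix 2 should also state which one governs, consistent with Section 6.3. Which mg dose is right is for the sponsor to settle.

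The cost is one or two sentences in Appendix 2. No change to the planned analyses is needed.

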# APPENDIX 3 EXAMPLES OF IN VIVO SUBSTRATES, INHIBITORS, AND INDUCERS FOR SPECIFIC ENZYMES

CYP	Substrate (sensitive)	Inhibitor (strong)	Inducer (strong)
2D6	atomoxetine, desipramine, dextromethorphan, eliglustat, nortriptyline, tolterodine, nebivolol, perphenazine, venlafaxine	bupropion, fluoxetine, paroxetine, quinidine, terbinafine	none identified
3A4/ 3A5	remifentanil, avanafil, buspirone, conivaptan, darifenacin, darunavir, ebastine, everolimus, ibrutinib, lomitapide, lovastatin, midazolam, naloxegol, nisoldipine, saquinavir, simvastatin, sirolimus, tacrolimus, tipranavir, triazolam, vardenafil	boceprevir, cobicistat, conivaptan, grapefruit juice, itraconazole, ketoconazole, ritonavir, clarithromycin, diltiazem, idelalisib, nefazodone, nelfinavir	carbamazepine, enzalutamide, mitotane, phenytoin, rifampin, St. John's wort
2C9	celecoxib	none identified	none identified
2C19	S-mephenytoin, omeprazole	fluconazole, fluoxetine, fluvoxamine, ticlopidine	rifampin, ritonavir
2C8	repaglinide	clopidogrel, gemfibrozil	none identified

Source: https://www.fda.gov/Drugs/DevelopmentApprovalProcess/DevelopmentResources/ucm093664.htm (accessed 5 March 2019)

Note: This is not an exhaustive list.

Sensitive substrates are drugs that show an increase in AUC of ≥5-fold with strong index inhibitors of a given metabolic pathway in clinical DDI studies.

Strong, moderate, and weak inhibitors are drugs that increase the AUC of sensitive index substrates of a given metabolic pathway  $\geq$ 5-fold.

Strong inducers are drugs that decreases the AUC of sensitive index substrates of a given metabolic pathway by  $\geq 80\%$ .

# APPENDIX 4 EXAMPLES OF IN VIVO SUBSTRATES, INHIBITORS, AND INDUCERS OF P-GLYCOPROTEIN

Transporter	Clinical Substrates	Clinical Inhibitors
P-gp (Gene ABCB1)	dabigatran, digoxin, fexofenadine	amiodarone, carvedilol, clarithromycin, dronedarone, itraconazole, lapatinib, propafenone, quinidine, ranolazine, ritonavir, telaprevir, verapamil

Source: Guidance for Industry: Drug Interaction Studies – Study Design, Data Analysis, Implications for Dosing, and Labeling Recommendations.

(http://www fda.gov/downloads/Drugs/GuidanceComplianceRegulatoryInformation/Guidances/UCM292362.pdf) Not an exhaustive list. For an updated list, see the following link:

 $http://www\ fda.gov/Drugs/DevelopmentApprovalProcess/DevelopmentResources/DrugInteractionsLabeling/ucm080499\ htm.$ 

Criteria for selecting clinical substrates for P-gp are those which (1) result in AUC fold-increase  $\geq 2$  with verapamil or quinidine coadministration and (2) in vitro transport by P-gp expression systems, but not extensively metabolized.

Criteria for selecting in vivo inhibitors for P-gp are those which (1) AUC fold-increase of digoxin  $\geq$ 2 with coadministration and (2) in vitro inhibitor.

#### ANNEX 1

#### **PART A: ELIGIBILITY**

Patients (≥2 years old) with PROS or PS with documented PIK3CA or AKT1 somatic mutation will be enrolled in this study.

Patient accrual will occur over a period of approximately 30 months.

Patients must meet ALL of the inclusion criteria and NONE of the exclusion criteria to be enrolled.

#### **INCLUSION CRITERIA**

- 1. Signed informed consent, and when applicable, signed assent
- 2. Male or female patients  $\geq 2$  years old with BSA of  $\geq 0.33$  m^2
- 3. Have a clinical diagnosis of PROS or PS with documented somatic PIK3CA or AKT1 mutations
- 4. Archival or fresh overgrowth tissue sample available to be shipped to Sponsor or designee
- 5. Have poor prognosis, significant morbidity, and/or progressive disease (eg, worsening of the disease/increase in number or size of the overgrowth lesions in the last 12 months)
- 6. Have measurable disease (at least one overgrowth lesion that can be accurately measured in size by imaging and/or linear or circumference measure)
- 7. Adequate organ function as indicated by the following laboratory values:
  - a. Hematological
    - 1. Hgb depending on age:
      - 2-5 years male and female:  $\geq 10.0 \text{ g/dL}$
      - 6-9 years male and female:  $\geq 11.5 \text{ g/dL}$
      - 10-17 years female:  $\geq 11.0 \text{ g/dL}$
      - 10-17 years male:  $\ge 11.5 \text{ g/dL}$
      - >17 years male and female:  $\geq$ 10.0 g/dL
    - 2. HbA1c: ≤8% (≤64 mmol/mol)
    - 3. ANC:  $>1.5 \times 10^9/L$

- 4. Platelet count  $\geq 150 \times 10^9/L$
- b. Hepatic
  - 1. Total bilirubin ≤1.5 x ULN
  - 2. AST and ALT ≤3 x ULN
- c. Renal
  - 3. Serum creatinine depending on age:
    - 2-5 years male and female: maximum 0.50 mg/dL
    - 6-10 years male and female: maximum 0.59 mg/dL
    - 11-15 years male and female: maximum 1.2 mg/dL
    - >15 years male and female: maximum 1.5 mg/dL
- d. Metabolic (lipids)
  - 1. Cholesterol:  $\leq 400 \text{ mg/dL}$  ( $\leq 10.34 \text{ mmol/L}$ )
  - 2. Triglyceride: ≤500 mg/dL (≤5.7 mmol/L)
- 8. If a female is of child-bearing potential, documentation of a negative pregnancy test is required before enrollment. Sexually active patients (male and female) must agree to use double-barrier contraceptive measures, oral contraception, or avoidance of intercourse while on study and for up to 90 days after ending treatment
- 9. Ability to complete the QoL questionnaires by the patient or his/her caregiver

#### **EXCLUSION CRITERIA**

- 1. History of Type 1 or 2 uncontrolled diabetes mellitus requiring regular medication (other than metformin or other oral hypoglycemic agents) or fasting glucose ≥160 mg/dL (if >12 years old) and ≥180 mg/dL (if ≤12 years old) at the Screening Visit
- 2. History of significant cardiac disorders:
  - Myocardial infarction or congestive heart failure defined as Class II to IV per the NYHA classification within 6 months of the first dose of miransertib (MI occurring >6 months of the first dose of miransertib will be permitted)
  - Grade 2 (per the current version of the NCI CTCAE) or worse conduction defect (eg, right or left bundle branch block).

#### PROTOCOL/AMENDMENT NO.: 002-07

- 3. Major surgical operation, radiotherapy, or immunotherapy within 4 weeks of the first dose of miransertib
- 4. Any experimental systemic therapy for the purpose of treating PROS or PS (eg, sirolimus, everolimus, high dose steroids) within 2 weeks of the first dose of miransertib, except for patients who were previously or are currently treated with miransertib under a Compassionate Use/Expanded Access program
  - Patients, who were previously treated with or currently are receiving miransertib, will be enrolled and treated according to the Schedule of Events/Study Visits defined in this protocol
- 5. Intolerance of or severe toxicity attributed to AKT inhibitors (eg, miransertib, uprosertib, afuresertib, ipatasertib)
- 6. Concurrent severe uncontrolled illness not related to PROS or PS
  - Ongoing or active infection
  - Known HIV infection
  - Malabsorption syndrome
  - Psychiatric illness/substance abuse/social situation that would limit compliance with study requirements
- 7. Pregnant or breastfeeding
- 8. Inability to comply with study evaluations or to follow drug administration guidelines

## **Schedule of Events Part A**

This table is intended as a cumulative list of visits and associated assessments.

Phase	Screening		Treat	ment (Year 1)		Treatment (Y	ears 2-4)		Follow-U	р
Tests & Procedures / Visit Name	Screening	C1D1	C1D15 C4D15 C7D15	C2, C3, C5, C6, C8, C9, C11, C12 Day 1	C4D1 C7D1 C10D1 C13D1	C16, C19, C22, C28, C31, C34, C40, C43, C46 Day 1	C25D1 C37D1	ЕОТ	30-day Safety Follow-up	3 Month Follow-up
Window (days)	-14 to 0	-1 to 0	± 3	± 5	± 5	± 5	± 5	Within 7 days	30+ days	±14 days
Written informed consent	X									
Medical history	X									
Physical examination	X	X	X	X	X	X	X	X		X
Vital Signs	X	X	X	X	X	X	X	X		X
Calculate BSA / dose		X		X	X	X	X			
12-Lead ECG	X			X	X	X	X	X		X
Fasting clinical blood tests	X			X	X	Х	X	X		X
Insulin/glucose blood tests			X							
Urinalysis	X				X	X	X	X		X
Serum pregnancy test (if applicable)	X							X		X
Disease Measurement	X				X					
Dispense miransertib		X		X	X	X	X			
Collect and count returned miransertib				X	X	X	X	X		

Phase	Screening		Treati	nent (Year 1)		Treatment (Y	ears 2-4)		Follow-U	p
Tests & Procedures / Visit Name	Screening	C1D1	C1D15 C4D15 C7D15	C2, C3, C5, C6, C8, C9, C11, C12 Day 1	C4D1 C7D1 C10D1 C13D1	C16, C19, C22, C28, C31, C34, C40, C43, C46 Day 1	C25D1 C37D1	ЕОТ	30-day Safety Follow-up	3 Month Follow-up
Window (days)	-14 to 0	-1 to 0	± 3	± 5	± 5	± 5	± 5	Within 7 days	30+ days	±14 days
Concomitant medications	X	X	X	X	X	X	X	X	X	X
Adverse events		X	X	X	X	X	X	X	X	X

<sup>1 C4D15 visit will only occur if the dose (mg/m²) increases at Cycle 4. C7D15 visit will only occur if the dose (mg/m²) increases at Cycle 7.

<sup>2 CYP2D6 at C1D15 ONLY. If not collected at C1D15 for previously enrolled participants, it will be collected at the next Cycle visit after reconsenting under the amended protocol.

<sup>3 ECG and PK are tested at C2D1 for all participants and at C5D1 and C8D1 only if the dose was increased at Cycle 4 and Cycle 7, respectively.

<sup>4 Blood for PK ONLY collected at C4D1 and C7D1.

<sup>5 Disease Measurement by US, photography and/or video recording only on C4D1 if no dose increase.

<sup>6 Dispense 3-cycle supply of drug at C13D1 if participant is continuing beyond the first 12 cycles of therapy.

<sup>7 ECGs will only be performed if clinically indicated or if required per standard of care.

# Study Visits – Screening Visit, Cycle 1 Day 1, and Cycle 1 Day 15 at 15 mg/m² Of Miransertib

	Screening visit (-14 – 0 days)	Cycle 1 Day 1 (15 mg/m²)	Cycle 1 Day 15 (± 3 days) (15 mg/m²)
the first dose  Medical histo Physical exan  Vital signs (herespiration ra  12-lead ECG Fasting Clini Serum pregna Biopsy of own biopsy sampl or if archival designee (for collected after The biopsy of but must mee  Disease mean photography, circumference dose of miran	mination, including skin.  neight, weight, temperature, blood pressure, ate, and heart rate).  cal Blood Tests Urinalysis.  ancy test, if applicable.  ergrowth tissue to confirm eligibility (if a prior le is not available to confirm genetic alteration) tissue is not available to ship to the Sponsor or previously enrolled participants, it will be er re consenting under the amended protocol).  an be performed >14 days before the first dose et the requirements for this protocol.  surement by imaging (eg, MRI, CT, US, y video recording) and/or by other the measurements within 28 days before the first	Physical examination, including (If Screening Visit was within 3 days of C1D1, physical examination does not have to be repeated)  Vital signs (height, weight, temperature, blood pressure, respiration rate, and heart rate)  Calculate BSA using the DuBois formula  Blood sample for potential biomarkers, including fibrinogen and D-dimers  Dispense miransertib and administer the first dose after all assessments listed above are completed (other than postdose blood draws)  Record concomitant medication  Assess AEs after the first dose	Physical examination, including skin Vital signs (temperature, blood pressure, respiration rate, and heart rate) Blood sample for insulin/glucose Record concomitant medication Assess AEs

# Study Visits – Cycle 2 Day 1 to Cycle 13 Day 1

Cycles 2, 3, 5, 6, 8, 9, 11 and 12 - Day 1 (± 5 days) (*when dose did not change either at C4 or at C7 respectively)	Cycles 4 and 10 - Day 1 (± 5 days) (C4 dose not changed)	Cycles 7 and 13 - Day 1 (± 5 days) (C7 dose not changed)

 
Physical examination, including skin
 
Vital signs (height, weight, temperature, blood pressure, respiration rate, and heart rate)
 
Calculate BSA using the DuBois formula
 
12-lead ECG, predose (ONLY Cycle 2 Day 1)
 
Fasting Clinical Blood Tests
 
Where relevant, additional functional test(s) to evaluate individual participant disease status – frequency as per standard of care
 
Dispense miransertib
 
Collect and count returned miransertib
 
Record concomitant medication
 
Assess AEs
 
	
 
Physical examination, including skin
 
Vital signs (height, weight, temperature, blood pressure, respiration rate, and heart rate)
 
Calculate BSA using the DuBois formula
 
12-lead ECG, predose
 
Fasting Clinical Blood Tests Urinalysis
 
Fibrinogen and D-dimers
 
Dispense miransertib
 
Collect and count returned miransertib
 
Record concomitant medication
 
Assess AEs
 
	
 
Physical examination, including skin
 
Vital signs (height, weight, temperature, blood pressure, respiration rate, and heart rate)
 
Calculate BSA using the DuBois formula
 
12-lead ECG, predose
 
Fasting Clinical Blood Tests Urinalysis
 
Optional lesion biopsy (ONLY Cycle 13)
 
Fibrinogen and D-dimers
 
Where relevant, additional functional test(s) to evaluate individual participant disease status – frequency as per standard of care
 
Dispense miransertib (dispense 3-cycle supply at C13 if participant is continuing beyond first 12 cycles of treatment)
 
Collect and count returned miransertib
 
Record concomitant medication
 
Assess AEs
 

